6.14.1. Unscheduled Visits

Unscheduled visits may be necessary during the course of the study to capture a subject's status between regularly scheduled visits. Examples include, but are not limited to, a worsening of psoriasis symptoms, occurrence of an AE, or follow-up to a previously reported AE.

The following assessments will be performed at these visits:

- Assess vital signs (temperature, respiratory rate, pulse, and seated blood pressure) and weight
- Record concomitant medications and AEs
- Drug accountability
- PASI

The following assessments may also be performed at the discretion of the Investigator, if clinically needed:

- Obtain blood sample and/or urine sample for any necessary laboratory test indicated in the Table of Events, Section 5
- Perform abbreviated physical examination

6.15. Blood Collection for Pharmacokinetic Analysis

Blood samples will be collected through an indwelling venous cannula, by direct venipuncture or by finger sticks at pre-specified time points for measurement of apremilast in plasma and/or blood. Concentrations of apremilast in plasma or blood will be measured using a validated liquid chromatography tandem mass spectrometry assay and dried blood spot (DBS) assay,

respectively. Specific details regarding the collection, processing, storage, and shipment of all PK samples are provided in Section 19, Appendix F.

Pharmacokinetic blood draws will be performed at the following nominal time(s):

Group 1 (ages 12 to 17 years, inclusive):

Day 1: 2 hours post morning dose.

Day 14 (last dose of PK treatment period): Predose (prior to morning dose), 1, 2, 3, 5, 8, and 12 hours after the morning dose.

Group 1 Notes:

- For Group 1 subjects, a DBS will be collected by fingerstick in parallel (each time point) to the standard plasma PK sample collection. Detailed instructions for the collection and processing are provided in Section 19, Appendix F. Plasma sampling may be discontinued from the protocol procedure at anytime, per the direct instruction of the Sponsor, in the situation that the DBS sample collection method is comparable to the plasma sample collection method.

Group 2 (ages 6 to 11 years, inclusive):

Day 1: 2 hours post morning dose.

Day 14 (last dose of PK treatment period): Predose (prior to morning dose), and 2, 5, and 12 hours post morning dose.

Group 2 Notes:

- If the DBS assay using minimal blood volume is verified during Group 1 study conduct, the DBS assay may be used in place of the plasma PK sampling for the balance of Group 1 and any subject in Group 2. If the DBS assay is not acceptable, DBS will be discontinued from the protocol procedure per the direct instruction of the Sponsor, and thus only the standard plasma PK sampling will be used for the duration of the study.

Actual PK blood sample collection times will be recorded in the source documents and eCRF. Explanations should be provided in the source documents and eCRF for missed or mishandled samples and for samples collected outside the acceptable time window as described in Table 2.

All enrolled subjects who take at least one dose of apremilast and have evaluable PK data will be included in the PK analysis. Pharmacokinetic data is considered evaluable if there are measurable drug levels of apremilast in plasma from at least 3 time points which extend over a minimal 5-hour period within 12 hours post a dose, eg, predose, 2 and 8 hours post a dose.

Table 2: Acceptable Time Windows for Pharmacokinetic Blood Sampling

Scheduled PK Blood Draw Time	Acceptable Time Window
Predose	Within 60 minutes prior to dosing
0 to 3 hours postdose (inclusive)	± 5 minutes
4 to 12 hours postdose (inclusive)	± 10 minutes

PK = pharmacokinetic.

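### The evaluability rule and the non-compartmental input accept plasma only, so if the optional switch to dried blood spot is used, DBS-only subjects fall outside the PK population as written

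*Protocol*

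**What the plan says.** Protocol 6.15 sets up two assays for two matrices: "apremilast in plasma or blood will be measured using a validated liquid chromatography tandem mass spectrometry assay and dried blood spot (DBS) assay". The two lists are paired in order, so plasma goes with the mass spectrometry assay and blood with DBS.

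In Group 1 both are taken: "a DBS will be collected by fingerstick in parallel (each time point) to the standard plasma PK sample collection". Two provisions then allow plasma to be dropped:

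- Group 1 Notes: "Plasma sampling may be discontinued from the protocol procedure at anytime, per the direct instruction of the Sponsor". The condition attached is that DBS collection has proved comparable with plasma collection.
- The notes for Group 2 set the condition "If the DBS assay using minimal blood volume is verified during Group 1 study conduct" and, where it is met, allow that "the DBS assay may be used in place of the plasma PK sampling for the balance of Group 1 and any subject in Group 2". Should DBS prove unacceptable, the study stays with plasma only.

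Later in 6.15, PK data count as evaluable only with "measurable drug levels of apremilast in plasma from at least 3 time points which extend over a minimal 5-hour period", inside the 12 hours after a dose. The Summary (Statistical Methods) and 10.2 repeat the plasma condition. The Summary bases the PK analyses on the population so defined, and the Summary and 10.8 both name plasma concentrations as the non-compartmental input. Section 3.1 defines the peak concentration, the areas under the curve and apparent clearance as plasma quantities. Section 10.3 sets a floor of 32 subjects with evaluable PK data and provides for replacing dropouts.

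The general sampling statements are wider. Section 6.15 describes collection "for measurement of apremilast in plasma and/or blood", and the Summary's PK overview also names both matrices.

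**The concern.** The protocol authorises a sampling path that its own population definition does not recognise. A child sampled only by DBS, with full compliance and a complete profile, fails the evaluability rule because no plasma was drawn.

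PK is part of the primary objective, which is to select a pediatric dose, and 10.9 aims for exposure similar to that of adults on 30 mg BID. The younger group is the one most exposed to the mismatch. It is sampled after Group 1, so verification may already be complete, and the substitution clause covers any of its members. If the switch were made, following the protocol literally would exclude subjects sampled by an approved method. Including them would depart from the population definition that the protocol states.

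**Working it through.** There is no sample-size formula to reproduce, since 10.3 says that no formal calculation was made. The planned total agrees with its parts: 16 + 16 = 32 (7.1, 10.3).

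**Step 1: does a DBS-only subject meet the rule?**

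| | Day 14 samples (6.15) | Plasma time points if DBS-only | Required |
|---|---|---|---|
| Group 1 | predose, 1, 2, 3, 5, 8, 12 h = 7 | 0 | 3 |
| Group 2 | predose, 2, 5, 12 h = 4 | 0 | 3 |

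A subject with plasma at the single Day 1 time point and DBS afterwards has 1 plasma time point and also fails.

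**Step 2: does any statement admit DBS values?** The plasma condition appears in the Summary, 6.15 and 10.2, and the plasma input in the Summary and 10.8. None of these accepts blood or DBS concentrations, treats them as plasma values, or gives a conversion. Only the general sampling statements in the Summary and 6.15 mention blood.

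**Step 3: effect on the count.** Let N be the number enrolled and d the number who are DBS-only, with no dropouts.

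- Evaluable as written = N − d
- Shortfall against 10.3 = max(0, 32 − (N − d))

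At the minimum N = 32:

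- Plasma kept throughout, d = 0: 32 evaluable, shortfall 0.
- All of Group 2 DBS-only and all of Group 1 with plasma, d = 16: 32 − 16 = 16 evaluable, shortfall 16. In ages 6 to 11, 16 − 16 = 0 are evaluable.

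The protocol fixes neither when a switch would happen nor how widely, so d is unknown and the second line is an example. Because 32 is a minimum, extra enrolment could offset some of the shortfall. The replacement provision names dropouts, and a DBS-only completer is not one.

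**Step 4: would the same samples pass if DBS were admitted?** Yes, if levels are measurable. Group 2's 4 Day 14 samples run from predose to 12 h, against 3 time points over 5 hours, and Group 1's 7 cover the same span. At N = 32 up to 32 would be evaluable under any switch.

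**Step 5: data available to link the matrices.** Paired samples per Group 1 subject = 1 (Day 1, 2 h) + 7 (Day 14) = 8, so at most 16 × 8 = 128 if all 16 are sampled both ways. None is planned in Group 2.

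**The case against.** The strongest reply is that this is a contingent wording mismatch with an obvious intent. The switch needs a successful verification or comparability result and then a choice by the sponsor. A method that replaces plasma sampling, having been found comparable to it, would naturally be read as standing in for plasma. Conversion and operational population rules usually belong in the SAP, which is not shown.

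Much of this stands. The defect is conditional, the intent is evident, and conversion details can go in the SAP. It does not remove the point. No section says that DBS values count as plasma values. The Group 2 clause asks only that the assay be verified, while comparability is the condition in the Group 1 clause. The protocol itself fixes the population and the input as plasma, so a SAP that accepted DBS would differ from it.

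Three stronger readings are tempting, and the documents do not support them:

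- *The trial will lose half its PK subjects.* That follows only if every Group 2 subject is DBS-only and the rule is applied literally. Nothing shows how likely the switch is.
- *No rule for DBS data exists.* This cannot be shown with the SAP unseen.
- *The staged dose decisions are blocked.* Section 10.9 and the DMC provisions refer to PK data generally and do not restate the plasma condition. The mismatch bears on the formal PK population and the analyses based on it.

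**Conclusion.** The point holds in conditional form and should be fixed. On a path that 6.15 authorises, the stated evaluability rule and non-compartmental input exclude each DBS-only subject, and each one lowers the evaluable count by one. With 32 enrolled, no dropouts and all of Group 2 DBS-only, 16 are evaluable and none is aged 6 to 11. If plasma is kept throughout, the loss is 0 and nothing conflicts.

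The conclusion rests on two things: the optional switch is used, and the definitions are applied as written. Confidence in the wording mismatch is high. The number of subjects that would actually be affected cannot be stated from the protocol. Since there is no formal sample-size calculation, no power or precision target fails. What is missed is the protocol's own floor of 32 evaluable subjects.

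**What to change.** 1. In the Summary, 6.15 and 10.2, define evaluable data as measurable levels in plasma, or in DBS once the existing 6.15 verification or comparability condition is met. Keep the present requirement of 3 or more time points spanning 5 hours or more within 12 hours after a dose.
2. In the Summary, 3.1 and 10.8, let the PK parameter definitions and the non-compartmental input use plasma values or DBS values. DBS values are used directly if shown comparable to plasma, and otherwise converted to plasma equivalents from the paired Group 1 samples.
3. In 10.9, put the comparison with adult exposure on the same footing.
4. Note that paired samples are planned only in ages 12 to 17, so applying the relationship to ages 6 to 11 is an extrapolation. Put the conversion details in the SAP.

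The cost is wording in the Summary, 3.1, 6.15, 10.2, 10.8 and 10.9. Any conversion would use paired samples already planned, so no new samples or visits are needed.

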6.16. Exploratory Assessments

6.16.1. Psoriasis Area Severity Index (PASI)

Psoriasis Area Severity Index scores will be determined for all subjects throughout the study. The PASI calculation is described in [Appendix G](#).

The PASI is a measure of psoriatic disease severity taking into account qualitative lesion characteristics (erythema, thickness, and scaling) and degree of skin surface area involvement on defined anatomical regions. The PASI is a validated instrument that has become standard in clinical trials for psoriasis.

Psoriasis Area Severity Index scores range from 0 to 72, with higher scores reflecting greater disease severity ([Fredriksson, 1978](#)). Erythema, thickness, and scaling are scored on a scale of 0 (none) to 4 (very severe) on 4 anatomic regions of the body: head, trunk, upper limbs, and lower limbs. Degree of involvement on each of the 4 anatomic regions is scored on a scale of 0 (no involvement) to 6 (90% to 100% involvement). The total qualitative score (sum of erythema, thickness, and scaling scores) is multiplied by the degree of involvement for each anatomic region and then multiplied by a constant. These values for each anatomic region are summed to yield the PASI score.

Measurements of PASI will be performed at Screening, Baseline and all following visits as indicated in the Table of Events (Section 5).

7. STUDY POPULATION

7.1. Number of Subjects and Sites

At least 32 subjects (16 subjects in Group 1 and 16 subjects in Group 2) with moderate to severe plaque psoriasis will be enrolled at approximately 20 sites in the United States, Canada and Europe.

7.2. Inclusion Criteria

Subjects must satisfy all of the following criteria to be enrolled in the study:

1. Male or female subjects 6 to 17 years of age, inclusive, at the time the informed consent document is signed by the legal guardian
2. **Group 1 Only:** ages 12 to 17 years, inclusive, and weighs ≥ 35 kg
3. **Group 2 Only:** ages 6 to 11 years, inclusive, and weighs ≥ 15 kg
4. Subject is able to swallow the apremilast tablet
5. Able to sign an assent with a legal guardian who can understand and voluntarily sign an informed consent
6. Able to adhere to the study visit schedule and other protocol requirements
7. Must agree to withhold vaccinations during the first 2 weeks of dosing. Inactivated vaccines will be allowed during the extension treatment period
8. Diagnosis of chronic plaque psoriasis for at least 6 months prior to Screening
9. Have moderate to severe plaque psoriasis at Screening and Baseline as defined by:
 - PASI score ≥ 12 ; and
 - Body surface area (BSA) $\geq 10\%$; and
 - sPGA ≥ 3 (moderate to severe)
10. Disease inadequately controlled by or inappropriate for topical therapy for psoriasis
11. Candidate for systemic or phototherapy
12. Have not been exposed to any or have been exposed to no more than one systemic agent for psoriasis
13. At Screening, laboratory values must be within the following ranges:
 - White blood cell (WBC) count

Age (yrs)	Males ($\times 10^3 / \mu\text{L}$)	Females ($\times 10^3 / \mu\text{L}$)
6-11	3.5 – 13.65	3.5 – 13.65
12-18	3.5 – 13.15	3.5 – 13.15

- Platelet count

Age (yrs)	Males (x 10 ³ /μL)	Females (x 10 ³ /μL)
6-11	117 – 394	117 - 394
12-18	126 – 400	126 - 400

- Serum creatinine ≤ 1.2 X upper limit of normal (ULN) for age and gender. Please see reference ranges of the central laboratory.
- AST (SGOT) and ALT (SGPT) ≤ 1.5 X ULN for age and gender. If initial test of ALT or AST is > 1.5 X ULN, one repeat test is allowed during screening. Please see reference ranges of the central laboratory.
- Total bilirubin ≤ 2 mg/dL (≤ 34 μmol/L). If initial test result is > 2 mg/dL, one repeat test is allowed during the screening period.
- Hemoglobin (Hb)

Age (yrs)	Males (g/dL)	Females (g/dL)
6-11	10.0 – 15.5	10.0 – 15.5
12-18	11.0 – 18.1	10.0 – 16.4

14. Male subjects who engage in activity in which conception is possible must use barrier contraception (male latex condom or nonlatex condom NOT made out of natural [animal] membrane [for example, polyurethane]) while on apremilast and for at least 28 days after the last dose of apremilast
15. All females of childbearing potential (FCBP) must either practice abstinence* from heterosexual contact or use one of the approved contraceptive options as described below while on apremilast and for at least 28 days after administration of the last dose of apremilast. For the purposes of this study, a female subject is considered of childbearing potential if she is ≥ 12 years old or has reached menarche, whichever occurred first

At the time of study entry, and at any time during the study when a female subject of childbearing potential's contraceptive measures or ability to become pregnant changes, the Investigator will educate the subject regarding abstinence or contraception options and the correct and consistent use of effective contraceptive methods in order to successfully prevent pregnancy

Females of childbearing potential must have a negative pregnancy test at Screening and Baseline. All FCBP who engage in activity in which conception is possible must use one of the approved contraceptive options described below:

Option 1: Any one of the following effective methods: hormonal contraception (oral, injection, implant, transdermal patch, vaginal ring); intrauterine device (IUD); tubal ligation; or partner's vasectomy;

OR

Option 2: Male or female condom (latex condom or nonlatex condom NOT made out of natural [animal] membrane [for example, polyurethane]); PLUS one additional barrier

method: (a) diaphragm with spermicide; (b) cervical cap with spermicide; or
(c) contraceptive sponge with spermicide

* Periodic abstinence (eg, calendar, ovulation, symptothermal, post-ovulation methods) and withdrawal are not acceptable methods of contraception.

7.3. Exclusion Criteria

The presence of any of the following will exclude a subject from enrollment:

1. History of or currently active inflammatory bowel disease
2. Major concurrent medical conditions, pregnancy or lactation
3. Any condition that confounds the ability to interpret data from the study
4. Guttate, erythrodermic, or pustular psoriasis
5. Psoriasis flare or rebound within 4 weeks prior to Screening
6. Evidence of skin conditions that would interfere with clinical assessments
7. History of human immunodeficiency virus infection, or positive result to hepatitis B surface antigen or hepatitis C antibodies at Screening
8. Clinically significant abnormality on 12-Lead ECG at Screening
9. History of active mycobacterial infection with any species (including *Mycobacterium tuberculosis*) within 3 years of the Screening Visit and without documentation of successful treatment
10. Congenital and acquired immunodeficiencies (eg, Common Variable Immunodeficiency), immunoglobulin A deficiency
11. History of recurrent significant infections
12. Active infection or infection treated with antibiotic treatment within 2 weeks of first dose
13. Any history of or active malignancy
14. History of allergy/intolerance to any component of the investigational product, ie, apremilast, lactose monohydrate, microcrystalline cellulose, croscarmellose sodium, magnesium stearate, hypromellose 15 cP, titanium dioxide, polydextrose FCC, talc, maltodextrin, medium chain triglycerides, iron oxide red, iron oxide yellow, and iron oxide black.
15. Deficiencies in lactose metabolism, ie, galactose-1-phosphate uridylyltransferase, UDP-galactose 4-epimerase, galactokinase or Fanconi Bickel syndrome, including congenital lactase deficiencies, and glucose-galactose malabsorption.
16. Any other significant medical condition, laboratory abnormality, or psychiatric illness that would prevent the subject from participating in the study or which places the subject at unacceptable risk if he/she were to participate in the study
17. Prior history of suicide attempt at any time in the subject's lifetime prior to screening or enrollment in the study or major psychiatric illness requiring hospitalization within 3 years

18. Answering “Yes” to any question on the Columbia-Suicide Severity Rating Scale during screening or at baseline
19. Having received biologic therapy within 5 terminal half-lives, including but not limited to the following time periods:
 - Four weeks prior to baseline for etanercept
 - Ten weeks prior to baseline for adalimumab
 - Twenty-four weeks prior to baseline for ustekinumab
20. Topical therapy within 2 weeks of baseline (including but not limited to topical corticosteroids, topical retinoid or vitamin D analog preparations, tacrolimus, pimecrolimus, or anthralin/dithranol)
 - Exceptions: low-potency corticosteroids (please refer to the Investigators’ Manual) will be allowed as background therapy for treatment of the face, axillae, and groin in accordance with the manufacturers’ suggested usage during the course of the study
 - Subjects with scalp psoriasis will be permitted to use coal tar shampoo and/or salicylic acid scalp preparations on scalp lesions
 - An unmedicated skin moisturizer (eg, Eucerin®) will be also permitted for body lesions only. Subjects should not use these topical treatments within 24 hours prior to the clinic visit
21. Systemic therapy for psoriasis within 4 weeks prior to baseline (including but not limited to cyclosporine, corticosteroids, methotrexate, oral retinoids, mycophenolate, thioguanine, hydroxyurea, sirolimus, sulfasalazine, azathioprine, and fumaric acid esters)
22. Use of phototherapy (ie, UVB, PUVA) within 4 weeks prior to baseline
23. Use of any investigational drug within 4 weeks prior to baseline, or 5 pharmacokinetic/pharmacodynamic half-lives, if known (whichever is longer)
24. Children in Care: a child who has been placed under the control or protection of an agency, organization, institution or entity by the courts, the government or a government body, acting in accordance with powers conferred on them by law or regulation
25. Prior treatment with apremilast

8. DESCRIPTION OF STUDY TREATMENTS

8.1. Description of Investigational Product(s)

Sufficient quantities of apremilast will be supplied by Celgene and should be stored as directed on the label. Apremilast will be supplied in tablets with the following strengths: 10 mg, 20 mg and 30 mg for oral administration only. All dose strengths will be supplied to the sites in bottles or equivalent. The excipients contained in the apremilast tablets used in this study are listed in Section 7.3 (exclusion criterion #14). Refer to the Investigator's Brochure for additional detailed information regarding apremilast.

8.2. Treatment Administration and Schedule

On PK days (Day 1 and Day 14), all subjects will be administered the morning dose of apremilast by mouth in the fasted state. Food and beverages (except water) will be withheld from subjects for at least 8 hours prior to the morning dose until at least 2 hours after the morning dose. All apremilast administered while the subject is in the clinic will be administered by trained staff with approximately 240 mL of noncarbonated, room temperature water or as much as needed to ensure apremilast is swallowed. The person responsible for dosing will check the subject's mouth to ensure that the formulation has been swallowed intact.

For all evening doses and all morning doses administered on non-PK days, apremilast tablets will be taken approximately 12 hours apart and without any food restrictions. Apremilast tablets should always be taken with water as described in the previous paragraph. Dosing regimens may vary depending on dose strength/dose frequency determined from the Group 1 and Group 2 PK and safety data. See Section 6.8 for additional details concerning oral dosing of apremilast.

The sponsor may provide financial assistance for overnight accommodations near the study site before and/or on PK blood draw visit days for the sake of subject convenience.

8.2.1. Overdose

Overdose, as defined for this protocol, applies to protocol-required dosing of apremilast. Overdose for this protocol, on a per dose basis, is defined as ingestion of greater than 100 mg of apremilast tablets in any specific dosing period (ie, 24 hours) whether by accident or intentionally. Adverse events associated with an overdose must be collected on the Adverse Events page of the eCRF (see Section 11.1) for all overdosed subjects, but the overdose itself is not considered an AE. Other required or optional nonstudy drugs intended for prophylaxis of certain side effects, etc, are excluded from this definition.

Detailed information about any Celgene drug overdose in this study, regardless of whether the overdose was accidental or intentional, should be reported on the drug exposure eCRF page.

